## STUDY SYNOPSIS

Title:	A Double Blind Randomized Placebo Controlled Study of CM-AT for the Treatment of Autism in Children With All Levels of Fecal Chymotrypsin
Protocol Number:	00103
Development Phase:	III
Number of Study Centers:	Approximately 35 clinical sites in the United States
Number of Subjects:	Approximately three-hundred (300) patients will be randomized
Estimated Study Length:	Approximately 36 months, contingent upon meeting accrual targets
Duration of Treatment and Study Participation:	12 weeks, following a 2-week blinded drug run-in period.
Patient Population:	The study population will consist of children, both males and females, between 3 and 8 years of age inclusive at the time of consent, who are diagnosed with Autistic Disorder (AD) by DSM-IV-TR and ADI-R, and are screened by the SCQ.
Test Product, Dose, and Mode of Administration:	CM-AT (pancreatic enzyme concentrate encapsulated in hydrogenated soybean oil) 900mg 3x daily sprinkled over food. To be taken with a meal or large snack.
Study Methodology:	This is a Phase III multi-center, randomized, double-blind, placebo-controlled study evaluating the efficacy and safety of CM-AT in pediatric patients with autism at all levels of fecal chymotrypsin.
Study Design:	In this Phase III multi-center, randomized, double-blind, placebo-controlled study, all study participants must have an initial ABC-I score of $\geq 11$ and a diagnosis of Autistic Disorder as demonstrated by the DSM-IV-TR and by the ADI-R. Subjects will also be screened using the SCQ and must achieve a score of $\geq 15$ to be considered eligible. Those subjects who qualify will be given a two week blinded drug run-in. Subjects will then be evaluated for compliance and re-evaluated for level of Irritability with the ABC-I scale. If their score on the ABC-I scale has increased by 30% or more or decreased by 30% or more, or is <9, they will be discontinued from the study.
Study Rationale:	Sponsor studies have demonstrated the clinical potential of CM-AT formulations in treating core and non-core autism symptoms in subjects with autism ages 3-8 with low fecal chymotrypsin (FCT) levels when dosed at a level of 900mg 3x daily.  This study will further quantify the changes in the target population as measured by standardized behavioral and quality of life tests, physiological measures, as well as characterize the efficacy and safety of the product. The study will further delineate the efficacy in a population that is biomarker negative (>12.6U/g of fecal chymotrypsin) who have autism.  The data from this study will help determine safety and efficacy of CM-AT in pediatric patients with autism of both biomarkers positive and negative.

	This study will be undertaken in children whose Aberrant Behavior Checklist: subscale for Irritability / Agitation (ABC-I) ≥11 is at Screening/Enrollment. This number represents those who fall above approximately 0.5 std deviations from the mean seen in the Sponsor's 00101 study.
Safety:	Fecal globin levels, the presence of occult blood, α 1 -antitrypsin, and weight loss will be used to monitor the safety and tolerability of CM-AT.
	
 
The presence of fecal globin may indicate bleeding in the large intestine, while a positive occult blood may indicate bleeding along the entire gastrointestinal tract.
 

	• An increase in α 1 -antitrypsin may signal an immunologic response of the colonic mucosa, leading to potential formation of colonic strictures.
	Weight loss may be indicative of malabsorption.
	
 
All of the above markers may be linked due to gastrointestinal irritation, but have not specifically been noted thus far in the Sponsor's experience with enzyme therapies.
 

	
 
Parental input at the standard visits, diary entries, and other assessments will also be used to monitor safety.
 

	
 
Of 468 children with autism given pancreatic enzymes in early Sponsor studies, and in the Phase III clinical studies (00101 & 00102), in which 180 were initially enrolled, and 140 continued into Open-Label, the drug appeared to be safe and well-tolerated with no related SAE experienced in either study the duration of which has been greater than 288 weeks. Primarily, AEs appeared to be GI in nature.
 

Rating Instruments:	ABC, SRS-2 (Preschool or School Age), PedsQL Inventory – Family Impact Module, CGI (S), CGI (I).
	Other measures: DSM-IV, SCQ and ADI-R.
Study Objectives:	Endpoint (outcome) measurements for treatment with CM-AT versus placebo in biomarker negative and positive subjects will be analyzed as described in Statistical Considerations.
	PRIMARY ENDPOINT MEASUREMENTS
	• Aberrant Behavior Checklist: subscale of Irritability/Agitation (ABC-I) at FCT levels ≤ 12.6
	SECONDARY ENDPOINT MEASUREMENTS
	
 
Aberrant Behavior Checklist: subscale of Lethargy/Social Withdrawal (ABC-L) at FCT levels ≤ 12.6
 

	EXPLORATORY ENDPOINT MEASUREMENTS
	Behavioral changes:
	(ABC-I) at FCT levels > 12.6
	
 
Aberrant Behavior Checklist: subscale of Lethargy/Social Withdrawal (ABC-L) at FCT levels > 12.6
 

	o Aberrant Behavior Checklist: subscale of Hyperactivity (ABC-H)
	at FCT levels ≤ 12.6  O Aberrant Behavior Checklist: subscale of Total (ABC-T) at FCT levels ≤ 12.6

	
 
Aberrant Behavior Checklist: subscale of Stereotypy (ABC-S) at FCT levels ≤ 12.6
 
Aberrant Behavior Checklist: subscale of Inappropriate Speech
 

	(ABC-IS) at FCT levels ≤ 12.6  ○ Aberrant Behavior Checklist: subscale of Irritability/Agitation
	
 
(ABC-I) at all FCT levels
 
Aberrant Behavior Checklist: subscale of Lethargy/Social
 
Withdrawal (ABC-L) at all FCT levels
 

	
 
Aberrant Behavior Checklist: subscale of Hyperactivity (ABC-H) at all FCT levels
 

	
 
Aberrant Behavior Checklist: subscale of Total (ABC-T) at all FCT levels
 

	
 
Aberrant Behavior Checklist: subscale of Stereotypy (ABC-S) at all FCT levels
 

	
 
Aberrant Behavior Checklist: subscale of Inappropriate Speech (ABC-IS) at all FCT levels
 

	

Pediatric Quality of Life Inventory (PedsQL)

CGI-I, CGI-S

	o SRS-2
	GI health:     Stool Test Panel
	Weight gain/loss
	SAFETY ENDPOINT MEASUREMENTS
	
 
Adverse Events
 
Negative change in weight, if clinically inappropriate based upon standard scales
 

	
 
Incidence and/or change in clinical laboratory results for the following:
 
Fecal globin / Fecal occult blood
 

	
 
Stool pH
 
Presence or continued growth of pathogens, as indicated by stool panel antigen/toxin tests
 
Elevated α1-antitrypsin levels
 
Change in bowel habits due to colitis
 

Inclusion Criteria:	1. Age between 3 and 8 years, inclusive at the time of consent
	2. If the child is 7 years of age or older, understand and sign a written assent form or give witnessed verbal assent, if mental capacity allows
	3. The parent or guardian of the subject must be able to understand and sign a written informed consent document, a waiver of assent document (in some cases), and be able to read English
	4. Meets the current Diagnostic and Statistical Manual for Mental Disorders (DSM-IV-TR) diagnostic criteria for Autistic Disorder (AD), screened by the SCQ and confirmed by the ADI-R.
	5. Aberrant Behavior Checklist: subscale of Irritability/Agitation (ABC-I) score ≥11.0

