## Statistical Considerations:

The sample size is based on (a) the primary efficacy variable of the change from baseline to week 12 for the Aberrant Behavior Checklist (ABC) subscale for Irritability; (b) the primary analysis set of low-level fecal chymotrypsin (FCT)  $\leq$  12.6 Units/gram randomized subjects; and (c) a 1:1 randomization scheme. Assuming a mean  $\pm$  standard deviation decrease in ABC Irritability from baseline to week 12 of  $3.7 \pm 7$  for CM-AT and  $0.6 \pm 5$  for Placebo, a sample size of 82 evaluable low-level subjects per treatment group yields 90% power to declare a statistically significant difference between treatments at a two-sided 0.05 level of significance. Assuming 15% premature withdrawal, 97 low-level subjects will be randomized. In order to achieve 97 randomized low-level subjects per group, a total of 162 subjects per group will be randomized (based on previous data indicating 60% of autistic children are low-level).

Primary analyses (assessing CM-AT vs. Placebo difference) on change from baseline to week 12 will be estimated from a Mixed Model Repeated Measures (MMRM) across all visits assuming the unstructured within-subject correlation structure. Included in the model will be the main effects of randomized treatment group, visit, baseline ABC irritability, study center and the treatment-by-visit interaction effect. Analyses with and without imputation for missing data will be performed.

If statistical significance, in favor of CM-AT, is shown on the primary efficacy endpoint in the primary analysis set of low-level randomized patients (FCT  $\leq$  12.6 Units/gram), the study will be considered to be a success statistically. The secondary efficacy variable is change from baseline to week 12 in ABC Lethargy/ Social Withdrawal (ABC-L) of low-level randomized patients (FCT  $\leq$  12.6 Units/gram).

As an exploratory analysis, the MMRM analyses will be repeated on the ABC-I and ABC-L for the non-low-level FCT randomized patients (FCT > 12.6 Units/gram)

As an additional exploratory analysis, the above MMRM analyses will be repeated on the ABC-I and ABC-L on all randomized patients in a similar manner as for the low-level randomized patients.

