This is a Phase III, multi-center, randomized, double-blind, placebo-controlled study of approximately 300 subjects diagnosed with autism from approximately 35 clinical sites in the United States. Subjects will be between 3 and 8 years of age (inclusive) at the time of consent. All study participants must have an initial ABC-I score ≥ 11 and a diagnosis of Autistic Disorder as demonstrated by the Diagnostic and Statistical Manual for Mental Disorders IV Text Revision (DSM-IV-TR) and by the Autistic Diagnostic Interview − Revised (ADI-R). Subjects will also be screened using the Social Communication Questionnaire (SCQ) and must achieve a score ≥ 15 to be considered eligible.

After initial screening criteria are met, including the diagnosis of Autistic Disorder as demonstrated on the DSM-IV-TR, SCQ and ADI-R, the study participants will be administered the ABC. If their ABC-I score is greater than or equal to $11 (\geq 11)$ they can be enrolled and given a two-week initial blinded placebo run-in. At the end of the run-in, subjects will be evaluated and randomized if all inclusion criteria are satisfied.

The compliance and inclusion criteria required for randomization are: 1) subjects must take the study drug on the prescribed regimen and 2) continue to meet inclusion criteria. At the Visit 1 Visit, they will be reevaluated for their level of Irritability/Agitation with the ABC-I scale. If a subject's score on the ABC-I scale has increased or decreased by 30% or more, or is <9 on the retest, they will be discontinued from the study and not randomized. Qualified subjects can be randomized into the study if they meet all inclusion/exclusion criteria.

After enrolling in the study at a clinical site, subjects ultimately randomized to treatment will receive study drug or placebo three times daily with food for a

period of 12 weeks. Parents will keep a missed dose log. Subjects will be seen at Week 2, 4, 6, 8, 10, and 12, post-randomization. Standardized measures of behavior, health, and quality of life will be utilized. In addition, measures of overall health including growth and weight will be obtained.

Subjects will be randomized in a 1:1 ratio to CM-AT or Placebo (both biomarker negative (>12.6 U/g) and positive (≤12.6 U/g) will be included). Randomization will be based upon study drug vs placebo.

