Subjects will be randomized to ensure 82 subjects per study arm of the low-level fecal chymotrypsin (FCT) children are evaluable for the primary statistical analysis (treatment comparison on the primary endpoint of change in ABC irritability from Baseline to Week 12 on the primary analysis set of children with FCT \leq 12.6 in randomized subjects). The FCT value used in determination of whether the patient has FCT \leq 12.6 is the Screening Part 1 value; if the patient has more than one screening FCT, the last FCT measured prior to randomization will be used to determine whether the patient has FCT \leq 12.6. It is anticipated that each site will enroll approximately 3 to 5 subjects per month and the study will be open for a period of twelve months. A power recalculation may be performed midway through Study Protocol 00103 to determine if sufficient numbers of biomarker negative children have been enrolled.

A subject may enroll in Study Protocol 00104 Open Label Extension after successfully completing Week 12 of Study Protocol 00103. The analyses of data collected in Study Protocol 00104 Open Label Extension will be discussed in a separate analysis plan.

3. Study Analysis Sets

One-hundred sixty-two (162) subjects will be randomized per treatment arm, or 324 subjects total. These subjects will be randomized from approximately 35 sites throughout the United States. Approximately 350 subjects will be enrolled into the placebo run-in period to ensure that 324 will be randomized. At the completion of the two-week placebo run-in, the subject will be assessed for compliance and ABC-I scores. If a subject's score on the ABC-I scale has increased or decreased by 30% or more, or is <9 on the retest, they will be discontinued from the study and not randomized.

The study population will consist of children, both males and females, between 3 and 8 years of age inclusively at the time of consent. All study participants must have an initial ABC-I score of ≥ 11 and a diagnosis of Autistic Disorder as demonstrated by the DSM-IV-TR and by the ADI-R. Subjects will also be screened using the SCQ and must achieve a score of ≥ 15 to be considered eligible.

The following populations form the basis of the analysis sets that will be included in efficacy and safety analyses (not listed in order of analysis below. For order of analysis see Section 6.0):

Intent-to-Treat (ITT): All randomized subjects who received study drug and had at least one post-Baseline ABC-I assessment.

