Low-level FCT ITT: All randomized subjects with pathologically low levels of FCT (≤12.6 U/g) who received study drug and had at least one post-Baseline ABC-I assessment. Subjects are analyzed under the treatment to which they are randomized. This is the primary analysis population for efficacy.

Non-Low-Level FCT (FCT >12.6) ITT: All non-low-level (FCT >12.6 U/g) randomized subjects who received study drug and had at least one post-Baseline ABC-I assessment. Subjects are analyzed under the treatment to which they are randomized. This is an exploratory analysis population for efficacy.

All Randomized: All randomized subjects. This is an exploratory analysis population for efficacy. Subjects are analyzed under the treatment to which they are randomized.

Low-level FCT All Randomized Subjects: All randomized subjects with pathologically low levels of FCT (≤12.6 U/g). This is a population for use in a sensitivity analysis of efficacy. Subjects are analyzed under the treatment to which they are randomized.

Non-Low-Level FCT (FCT >12.6) All Randomized Subjects: All non-low-level (FCT >12.6 U/g) randomized subjects. Subjects are analyzed under the treatment to which they are randomized. This is an exploratory analysis population for efficacy.

Per-Protocol (PP): All ITT subjects who have completed a Week 12 visit and have a Week 12 ABC-I score. Subjects are analyzed under the treatment to which they are randomized. This is an exploratory analysis population for efficacy.

Low-Level FCT (FCT \leq 12.6) Per Protocol (PP): All low-level (FCT \leq 12.6 U/g) PP Subjects. Subjects are analyzed under the treatment to which they are randomized. This is an exploratory analysis population for efficacy.

Non-Low-Level FCT (FCT >12.6) PP: All non-low-level (FCT >12.6 U/g) PP Subjects. Subjects are analyzed under the treatment to which they are randomized. This is an exploratory analysis population for efficacy.

Run-in Analysis Set: All subjects receiving at least one dose of placebo during the placebo-run in phase. All subjects will be analyzed as one group.

Safety Analysis Set: All subjects receiving at least one dose of randomized treatment. Subjects are analyzed under the treatment received. This is a primary analysis set for safety.

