8.1 Sample Size

Sample size is based on:

- The primary efficacy variable -
 - Change from Baseline (score at Screening Part 1) to Week 12 for the Aberrant Behavior Checklist (ABC) subscale for Irritability
- The primary analysis set of Low-level FCT ITT subjects.
- 1:1 randomization scheme

Previously reported Sponsor data indicating that 60% of autistic children have pathologically low levels of FCT formed the basis for the following calculations. Assuming a -3.7 ± 7.0 ABC Irritability change from Baseline to Week 12 of for CM-AT and -0.6 ± 5.0 for Placebo, a sample size of 82 evaluable low-level subjects per treatment group (active and placebo) yields 90% power to declare a statistically significant difference between treatments at a two-sided 0.05 level of significance. To account for an anticipated 15% early withdrawal, 97 low-level subjects will be randomized per treatment group (active and placebo). A total of 162 subjects per group will be randomized to achieve 97 randomized low-level subjects per group (active and placebo).

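### The documents give two sample sizes, about 300 and 324 (162 per arm); only 324 follows from the plan's own calculation

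*Protocol*

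**What the plan says.** Two entries give the smaller figure. The protocol synopsis, Number of Subjects, says: "Approximately three-hundred (300) patients will be randomized". SAP Section 2 (Study Design) describes a "double-blind, placebo-controlled study of approximately 300 subjects diagnosed with autism from approximately 35 clinical sites".

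Three entries give the larger one:

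- Protocol, Statistical Considerations: "a total of 162 subjects per group will be randomized".
- SAP Section 3 (Study Analysis Sets): "One-hundred sixty-two (162) subjects will be randomized per treatment arm, or 324 subjects total". The same section sets the run-in intake from that total: "Approximately 350 subjects will be enrolled into the placebo run-in period to ensure that 324 will be randomized".
- SAP Section 8.1 (Sample Size): "A total of 162 subjects per group will be randomized to achieve 97 randomized low-level subjects per group". The preceding step is also there: "To account for an anticipated 15% early withdrawal, 97 low-level subjects will be randomized per treatment group".

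The figure 324 is printed as a total only in SAP Section 3. The other two places give 162 per group, so 324 there is 2 × 162. SAP Section 2 gives 300 as the size of the study, without saying in that phrase that this is the number randomised; the protocol synopsis does say so.

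**The concern.** Each document disagrees with itself about how many children are to be randomised, and no text reconciles the figures. The Number of Subjects line is the headline count in the protocol. The 162 per group comes from the power calculation for the primary endpoint in the low-FCT children. If recruitment were closed on the headline figure, the trial would on its own assumptions fall short of the 82 evaluable low-FCT children per arm on which the stated 90% power rests. SAP Section 9 also takes 82 per arm as the planned final evaluable size in the conditional-power formula, so the same number feeds the interim rule.

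**Working it through.** **Inputs** (protocol Statistical Considerations and SAP Section 8.1):

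- change in ABC-I of −3.7 (SD 7) on CM-AT and −0.6 (SD 5) on placebo
- two-sided 0.05, 1:1 allocation, 90% power
- 15% withdrawal, 60% low-FCT share

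**Reproducing the plan's figure**

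1. Difference = 3.7 − 0.6 = 3.1. Pooled SD = √((49 + 25)/2) = 6.083.
2. Two-sample t power at 82 per arm is 90.0% (normal approximation 90.4%). The smallest n per arm for 90% is 81.88 by the t calculation, so 82, as stated.
3. Withdrawal: 82 / 0.85 = 96.5, rounded up to 97 low-FCT children per arm.
4. Low-FCT share: 97 / 0.60 = 161.7, rounded up to 162 per arm.
5. Total: 2 × 162 = 324.

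Other ways of rounding or inflating do not lead to 300. Without rounding, 2 × 82 / 0.85 / 0.60 = 321.6. Multiplying by 1.15 instead of dividing by 0.85 gives 95 low-FCT children per arm and a total of about 317.

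**What each total delivers on the same rates** (evaluable per arm = total/2 × 0.60 × 0.85)

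| Total randomised | Low-FCT per arm | Evaluable per arm | Power (t) | Power (normal) |
|---|---|---|---|---|
| 300 | 90 | 76.5 | 87.9% | 88.3% |
| 324 | 97.2 | 82.6 | 90.3% | 90.6% |

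The gap is 324 − 300 = 24, and 24/324 = 7.4%.

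**How far the 88% depends on the assumptions** (300 randomised, t power). Each row changes one input. Values other than the plan's 15% and 60% are assumptions made for this check. The documents give no value for the correlation r between Baseline ABC-I and change; its effect is approximated by multiplying both variances by (1 − r²).

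| Input varied | Values and power | Reaches 90% at |
|---|---|---|
| Loss to the analysis | 15%: 87.9%; 10%: 89.7%; 5%: 91.2%; 0%: 92.5% | loss of 9.0% or less (1 − 81.88/90) |
| Low-FCT share, 15% loss | 55%: 85.0%; 60%: 87.9%; 65%: 90.3%; 70%: 92.3% | share of about 64% (82 / 0.85 / 150 = 0.643) |
| Correlation r, 15% loss | 0: 87.9%; 0.2: 89.2%; 0.3: 90.7%; 0.5: 95.1% | r of about 0.26 |

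**The case against.** The strongest reply is that the two figures are not equal rivals. Every place that derives the size gives 162 per arm, and the run-in intake is set to secure 324. The 300 entries are hedged descriptive lines that sit beside other approximate numbers, such as the site count. SAP Section 2 itself also says that randomisation is to secure 82 evaluable low-FCT children per arm. On that reading the headline total is a forecast, and the 88% arises only if 300 acts as a cap, which no text says. In addition, the primary set needs only children "who received study drug and had at least one post-Baseline ABC-I assessment", so some who withdraw still contribute, and the primary model adjusts for Baseline ABC-I. Either could bring the power at 300 back to 90% or more.

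Much of this stands as a limit on the consequence. The 88% is conditional on 300 being followed and on the plan's sizing assumptions. Nothing in the sample-size arithmetic itself is wrong, and a statistician would take 324 as operative. None of it reconciles the figures, however. The commitment to 82 evaluable per arm supports 324, because 300 does not deliver 82 at the plan's rates. A gap of 7.4% is more than rounding. The interim re-estimation in SAP Section 9 starts from 82 per arm and can only raise the size, so it does not explain 300. The possible mid-study power recalculation in SAP Section 2 concerns the number of biomarker-negative children and does not produce 300 either.

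**Conclusion.** The concern holds. The current text gives two sizes that differ by 24 children, and only 324 follows from the stated inputs. If 300 were the number randomised, power would be about 88% instead of 90%, with 5 to 6 fewer evaluable low-FCT children per arm (82 − 76.5 = 5.5). That result assumes 60% low-FCT, 15% lost to the analysis, the stated means and SDs, and no gain from baseline adjustment. The loss is modest and sensitive to those assumptions. The reason to act is that the headline count should match the calculation that justifies it; no endpoint, test, significance level or analysis set is affected.

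**What to change.** Replace about 300 with 324 (162 per arm) in the protocol synopsis, Number of Subjects, and in SAP Section 2. This changes the wording of two lines and leaves the planned size as it is.

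If the sponsor does intend 300, more has to change: restate the power as about 88% under the plan's sizing assumptions, and align the protocol's Statistical Considerations, SAP Section 2 (the commitment to 82 evaluable per arm), SAP Section 3 (including the run-in intake of about 350, which is tied to 324), SAP Section 8.1, and the value of 82 in the conditional-power formula of SAP Section 9.

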For continuous exploratory endpoints, treatments will be compared on change from Baseline in a similar manner as the primary endpoint at Week 12 and each Post-Baseline visit except for multiple imputation and assessment of treatment-by-study center interaction effects. For CGI-S, an endpoint for which there is no Baseline value, treatments will be compared in a similar manner as the primary endpoint on the CGI-S value itself (as opposed to a change from Baseline) without a Baseline value of the endpoint as a covariate. There will be no adjustment for multiple comparisons.

For dichotomous exploratory endpoints (stool test, weight gain/loss), no formal statistical hypothesis testing will be performed to compare the treatment groups on these results.

The number and percentage of subjects experiencing the dichotomous endpoint will be presented for each treatment group. For completeness, this analysis will be repeated for each visit.

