8.7 Safety Analyses

The safety analysis will be performed on the Run-in Safety Analysis Set (run-in phase safety data only) where specified, on the Low-Level FCT Safety Analysis set (for double-blind safety data) and on the entire Safety Analysis set (for double-blind safety data). All subjects receiving at least one dose of randomized treatment is the primary safety analysis set. There will be no imputation of missing data and there will be no adjustment for multiple comparisons.

Adverse Events – The number and percentage of subjects with TEAEs (Treatment Emergent Adverse Events) will be presented overall and by MedDRA System Organ Class (SOC) and Preferred Term (PT). Patients experiencing more than one occurrence of an event within a given SOC and PT will be counted only once within that SOC and PT, respectively. The analysis will be repeated for serious TEAEs, for TEAEs leading to premature withdrawal and for TEAEs deemed at least possibly related to study drug. No formal statistical hypothesis testing will be performed to compare the treatment groups on incidence of TEAEs.

The number and percentage of subjects with TEAEs will be presented by severity of TEAE (mild/moderate/severe) within each SOC and PT. A subject experiencing more than one occurrence of a TEAE within an SOC or

PT will be categorized under the maximum severity in which the subject experienced the TEAE.

The above will be repeated on the run-in TEAEs. The denominator will be the number of patients receiving placebo in the run-in phase, and there will only be one group analyzed (all patients receiving placebo in the run-in phase).

No formal statistical hypothesis testing will be performed to compare the treatment groups on the proportion of subjects with TEAEs.

Physical exams – The number and percentage of subjects with a clinically significant finding on the physical exams will be presented at each Post-Baseline double-blind visit. No formal statistical hypothesis testing will be performed to compare the treatment groups on the proportion of subjects with clinically significant findings.

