Fecal Panel - For Fecal Chymotrypsin, pH and A1-Antitrypsin, descriptive statistics (number of subjects, mean, median, standard deviation, minimum and maximum) of Baseline (Screening Part I), each Post-Baseline visit and the change from Baseline at each Post-Baseline visit will be presented. Treatment groups will be compared on change from baseline at each visit using analysis of covariance adjusting for study center and Baseline. For Fecal Chymotrypsin, the number and percentage of subjects with values >12.6 U/g and \le 12.6 U/g at each visit will be presented. For pH, the incidence rate (number and percentage of subjects) with abnormal outcomes will be presented at each visit. For A1-Antitrypsin, the number and percentage of subjects with values <55 and ≥55 will be presented at each visit. Further, for fecal globin and fecal occult blood the incidence rate (number and percentage of subjects) with abnormal outcomes will be presented at each visit, where abnormal is defined as the variable being "present". No formal statistical hypothesis testing will be performed to compare the treatment groups on these results.

Vital signs – For each of the following measurements: weight (kg), systolic blood pressure (mmHg), diastolic blood pressure (mmHg) and pulse (beats per minute), descriptive statistics (number of subjects, mean, median, standard deviation, minimum and maximum) of Baseline, each Post-Baseline visit and the change from Baseline at each Post-Baseline visit will be presented. No formal statistical hypothesis testing will be performed to compare the treatment groups on these results.

Weight Loss by End of Study - The number and percentage of subjects losing weight by the end of the study will be tabulated for each visit for each treatment group. No formal statistical hypothesis testing will be performed

to compare the treatment groups on the proportion of subjects with weight loss.

9. Interim Efficacy Analysis

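### Two safety endpoints in the protocol synopsis, stool pathogens and colitis-related bowel change, are not carried into the SAP's safety sections, and the planned tables cannot report them as defined

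*Protocol*

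**What the plan says.** The safety endpoint list in the protocol synopsis has seven items, taking fecal globin and occult blood as one. They are adverse events, negative weight change, globin/occult blood, stool pH, stool pathogens, elevated α1-antitrypsin and bowel-habit change. The two at issue read "Presence or continued growth of pathogens, as indicated by stool panel antigen/toxin tests" and "Change in bowel habits due to colitis". The same synopsis also lists the stool test panel among its exploratory endpoints.

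SAP Section 7 defines the safety parameters and Section 8.7 their analysis. Together they cover adverse events, physical examinations, fecal chymotrypsin, stool pH, fecal globin, occult blood, α1-antitrypsin, vital signs and weight loss. For the dichotomous stool markers the output is descriptive: "Further, for fecal globin and fecal occult blood the incidence rate (number and percentage of subjects) with abnormal outcomes" is to be shown at each visit.

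The C. difficile toxin, Cryptosporidium antigen and H. pylori antigen tests appear only in the stool and weight table of SAP Section 6.3, among the exploratory efficacy variables. Section 8.6.3 governs them: "For dichotomous exploratory endpoints (stool test, weight gain/loss), no formal statistical hypothesis testing will be performed", with counts and percentages by arm at each visit. Section 8.6 applies this to every ITT, All Randomized and PP set. The words bowel and colitis do not occur in the SAP.

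**The concern.** A reader who takes the protocol's safety list as the specification of the safety report will look for seven items in SAP 7 and 8.7 and find five.

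For pathogens, a table will exist but will not answer the question the protocol poses. Presence or continued growth refers to what happens to a child relative to Baseline: a new positive, or a positive that persists. A percentage positive at each visit is a marginal figure and contains neither. The table is also laid out by randomised arm, whereas the SAP presents the rest of its safety data by treatment received.

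For bowel change there is no variable, definition or dedicated output. Any grouping of adverse event terms to stand for it would have to be chosen after the data are seen. The protocol says that adverse events in earlier studies were mainly gastrointestinal, so this is an area where a pre-specified count is useful.

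**Working it through.** No stated figure has to be reproduced. The check sets the protocol's list against the SAP item by item, followed by two short arguments on what the planned tables can show.

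**Step 1: coverage.**

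| Protocol safety endpoint | SAP 7 and 8.7 | Elsewhere in the SAP |
|---|---|---|
| Adverse events | 7.1, 8.7 | none |
| Negative weight change | 7.6, 8.7 | 6.3 |
| Fecal globin / occult blood | 7.4, 8.7 | none |
| Stool pH | 7.3, 7.4, 8.7 | 6.3 |
| Stool pathogens | none | 6.3, 8.6.3 |
| Elevated α1-antitrypsin | 7.5, 8.7 | 6.3 |
| Colitis-related bowel change | none | none as such |

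Five of seven are covered and two are not. Weight counts as covered although the definitions differ: the protocol has "Negative change in weight, if clinically inappropriate based upon standard scales" and the SAP has "The number and percentage of subjects losing weight by the end of the study will be tabulated", without the qualifier.

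**Step 2: whether exploratory status explains the pathogen gap.** The stool and weight table in 6.3 has seven rows. Four of them (α1-antitrypsin, fecal chymotrypsin, pH, weight) are analysed again in 8.7. The three that are not are the three pathogen tests: 7 − 4 = 3. The SAP already reports panel items under both headings, so an exploratory listing does not by itself account for the absence.

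**Step 3: analysis sets.** Section 3 defines ITT, All Randomized and PP sets, each overall, for low-level and for non-low-level FCT. That is 3 × 3 = 9 efficacy sets on which 8.6 would tabulate the pathogen tests. Neither of the two double-blind safety sets, which are analysed by treatment received, is among them.

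**Step 4: what a by-visit percentage shows.** Take the planned 162 children in one arm (SAP 8.1). As an illustration only, since the documents give no pathogen rates, suppose 5 are positive at Baseline.

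- Case A: the same 5 remain positive. The later rate is 5/162 = 3.1%. Persistent 5, new 0.
- Case B: those 5 clear and 5 others become positive. The later rate is 5/162 = 3.1%. Persistent 0, new 5, or 5/(162 − 5) = 5/157 = 3.2% of those negative at Baseline.

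The planned table is identical in the two cases, while the quantities named in the endpoint are opposite.

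**Step 5: what the TEAE tables show for bowel change.** Section 8.7 counts a child once within each preferred term and once within each system organ class. If two relevant preferred terms have a and b children, the number of distinct children lies anywhere from max(a, b) to a + b, because one child may have both. The class total avoids double counting but mixes in every unrelated event of that class. Neither line gives the number of children with the endpoint.

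**The case against.** The strongest reply is that little is lost. The pathogen tests will be tabulated by arm and visit in the same descriptive form that 8.7 gives globin and occult blood. The All Randomized set contains every randomised child, so no treated child is omitted. It differs from the Safety Analysis Set only by children never dosed and any given the other arm's product, and nothing in the documents suggests those are many. All of this stands, and it rules out saying that the pathogens go unanalysed. It does not meet Step 4. Section 6.3 does mention abnormality status at each visit and change from Baseline to Week 12, but 8.6.3 promises no shift table for dichotomous results.

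A second reply is that the exploratory placement is the protocol's own. That also stands. A reader might infer that the SAP wrongly moved infection results into efficacy; the synopsis lists the panel under both headings, so the documents do not support that. Removing the tests from 6.3 would create a new mismatch.

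A third reply is that the safety paragraph of the protocol's Statistical Considerations names only globin, occult blood, α1-antitrypsin and weight loss, all of which are in 8.7. This is true, but the SAP did not treat that paragraph as a limit: stool pH is not named there and is analysed.

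A reader might also infer that the clinical sign of colonic stricture is being ignored. The protocol attaches that worry to α1-antitrypsin, an increase in which "may signal an immunologic response of the colonic mucosa, leading to potential formation of colonic strictures", and the SAP analyses α1-antitrypsin by value, by change and by threshold. The protocol does not present bowel habit as the sign of stricture. Bowel or colitis events that are reported as adverse events will also be tabulated by term, severity, seriousness and relatedness.

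**Conclusion.** The point holds in a limited form. Two of the seven protocol safety endpoints are not carried into SAP 7 and 8.7. For pathogens, counts will be available, but new and persistent positivity cannot be read from them and none is by treatment received. For bowel change, the component events will be available, but not a count of children.

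This is a gap in safety reporting that can be closed cheaply. The stronger statement, that these endpoints receive no analysis at all, is not supported.

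The verdict rests on three conditions. The figure of two in seven depends on reading globin and occult blood as one item and on treating the laboratory line as a heading. Only the protocol synopsis is available, so a fuller definition of the bowel-habit endpoint may exist in the protocol body; the SAP's silence stands either way. It is assumed that pathogen results are recorded per child at Baseline and after randomisation, as 6.3 indicates.

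**What to change.** Keep the three pathogen tests in 6.3 and cross-refer them to Sections 7 and 8.7. Add to 8.7, on the Safety Analysis Set and the Low-Level FCT Safety Analysis Set, by treatment received:

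1. For each pathogen test, the number of children negative at Baseline with any post-randomisation positive, and the number positive at Baseline who are still positive at their last test, each with its own denominator.
2. The number of children with at least one TEAE in a list of bowel-change and colitis preferred terms fixed before unblinding. Label it a grouped adverse event count, because a term list cannot show that a bowel change was due to colitis.

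If the sponsor does not intend these as safety endpoints, reconcile the protocol's safety list with the SAP and give the reason.

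The cost is a paragraph of SAP text and two or three descriptive tables from data already planned. No hypothesis test is added.
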